12.3 Always Serious Events

[figure not shown]
The following events must be reported as SAEs in accordance with Section 5.5.5 Reporting of Serious Adverse Events (SAEs).

- Acute liver failure
- Acute renal failure
- Acute respiratory failure
- Agranulocytosis
- Anaphylaxis
- Any malignancy
- Aplastic anaemia
- Confirmed or suspected transmission of infectious agents by marketed product
- Congenital anomalies
- Hepatic necrosis
- Malignant hypertension
- Pulmonary hypertension
- Convulsion
- Torsades de pointe
- Toxic epidermal necrolysis
- Ventricular fibrillation
- Haemolytic anaemia
- Bone marrow failure
- Myocardial infarction
- Cardiac arrest
- Deafness
- Blindess
- Pancreatitis acute
- Acute graft versus host disease
- Septic shock
- Sepsis
- Rhabdomyolysis
- Respiratory failure
- Stevens-Johnson syndrome

[figure not shown]
12.4 ECOG Performance Status

Performance Status Score

12.5 FACT–P

[figure not shown]

[figure not shown]
12.6 EQ-5D-5L

12.7 BPI-SF

12.8 BFI

(GPF 4.1J)

SAE	Serious Adverse Event
SAE	
	Safety Analysis Set
SAP	Statistical Analysis Plan
SOC	System Organ Class
SMQ	Standard MedDRA Query
TURP	Transurethral Resection of the Prostate

TTF1	Time to Treatment Failure 1
TTF2	Time to Treatment Failure 2
TTPP1	Time to PSA Progression 1
TTPP2	Time to PSA Progression 2
2nd TTPP	2nd Time to PSA Progression
ULN	Upper Limit of Normal
WHO-DD	World Health Organization Drug Dictionary

List of Key Terms

Terms	Definition of terms
Endpoint	A variable that pertains to the trial objectives
Variable	Any quantity that varies; any attribute, phenomenon or event that can have
	different qualitative or quantitative values.

1 INTRODUCTION

[figure not shown]
This Statistical Analysis Plan (SAP) contains a more technical and detailed elaboration of the principal features of the analysis described in the protocol, and includes detailed procedures for executing the statistical analysis of the primary and secondary endpoints and other data.

The SAP is finalized and signed prior to database hard lock.

This statistical analysis is prepared by and approved by the responsible biostatistician of Astellas Pharma Inc.. Any changes from the analyses planned in the SAP will be justified in the Clinical Study Report (CSR).

2 FLOW CHART AND VISIT SCHEDULE

Flow Chart

- *1: 28 days after final study treatment, or before starting other study drugs, or before starting other treatment for prostate cancer, whichever comes first
- *2: Subjects who discontinued the 1st line AAT due to PSA progression will start the 2nd line AAT within 6 weeks after the date of examination that identified PSA progression. Subjects who discontinued the 1st line AAT due to other reasons will start the 2nd line AAT within 6 weeks from the day when the investigator or subinvestigator decided the discontinuation.

Sponsor: Astellas Pharma Inc.
ISN/Protocol 9785-MA-3051
SAP Version 1.00

Table 1: Schedule of Assessments

1st line AAT

	Screening period	1st line AAT					Unscheduled*a
Visit Days	Days -28 to -7	1	29	57	85 and every subsequent 84 days	113 and every subsequent 28 days	-
Visit Weeks	−4 to −1	1	5	9	13 and every subsequent 12 weeks	17 and every subsequent 4 weeks	-
Allowed visit window (days)	-	_	± 7	± 7	± 7	± 7	_
Informed consent*b	X *b						
Subject background survey	X						
Confirmation of in/exclusion criteria	X	X					
Randomization/enrollment		X *c					
Vital signs*d	X	X	X	X	X	X	X
Height/body weight	X						
Laboratory tests*e	X	X	X	X	X	X	X
PSA	X	X			X	X	X
Abdominopelvic CT/MRI and bone scintigraphy (every 3 months)	X *f				X		X
Chest CT	X *f				X^{*g}		X
ECOG Performance Status	X	X	X	X	X	X	X
FACT-P		X			X		
EQ-5D-5L		X			X		
Brief Pain Inventory-Short Form (BPI-SF)*h	X	X			X		
Brief Fatigue Inventory (BFI)	X	X			X		
Adverse event survey*i		X	X	X	X	X	X
Survey on previous/concomitant medication	X	X	X	X	X	X	X
Study drug prescription (every month)		X	X	X	X	X	

CT: Computed Tomography, ECOG: Eastern Cooperative Oncology Group, FACT-P: Functional Assessment of Cancer Therapy–Prostate

^{*}a: Unscheduled visit may be made whenever adverse events should be assessed, or PSA progression and disease progression should be confirmed. Laboratory tests, PSA measurement, and diagnostic imaging will be performed when assessment is required.

^{*}b: Informed consent will be obtained within 42 days before enrollment (Day 1) and before initiating the scheduled study procedures.

^{*}c: Randomization should be performed on Day 1 after the confirmation of eligibility.

- ISN/Protocol 9785-MA-3051
- *d: Measure vital signs (blood pressure and pulse rate) at each visit.
- *e: Laboratory tests include hematology, biochemistry, blood glucose test, and urinalysis.
- *f: Imaging diagnosis performed before informed consent and within 42 days before randomization can be used as baseline data.
- *g: Not required if no chest metastasis is identified in the screening chest CT.
- *h: Instruct subjects to assess prostate cancer-related pains.
- *i: Collect all adverse events in the period from the start of study treatment to the date of safety follow-up visit.

2nd line AAT

Ziid iiic AA1	2nd line AAT			Unscheduled*1	At the end or discontinuation*2	Safety follow-up		
Visit Days	1	29	57	85 and every subsequent 84 days	113 and every subsequent 28 days	_	-	- -
Visit Weeks	1	5	9	13 and every subsequent 12 weeks	17 and every subsequent 4 weeks	_	Final treatment	28 days after final treatment*3
Allowed visit window (days)	-	± 7	± 7	± 7	± 7	_	Within 7 days after final treatment*11	± 7
Enrollment	X						X	
Vital signs*4	X	X	X	X	X	X	X	X
Laboratory tests *5	X	X	X	X	X	X	X	X
PSA	X			X	X	X	X	X
Abdominopelvic CT/MRI and bone scintigraphy (every 3 months)				X *6		X	X *12	
Chest CT				X *6,7		X	X *12	
ECOG Performance Status	X	X	X	X	X	X	X	X
FACT-P	X *8			X *8			X *12	
EQ-5D-5L	X *8			X *8			X *12	
Brief Pain Inventory-Short Form (BPI-SF) *9	X *8			X *8			X *12	
Brief Fatigue Inventory (BFI)	X *8			X *8			X *12	
Adverse event survey*10	X	X	X	X	X	X	X	X
Previous/concomitant medication	X	X	X	X	X	X	X	X
Study drug prescription (every month)	X	X	X	X	X			

CT: Computed Tomography, ECOG: Eastern Cooperative Oncology Group, FACT-P: Functional Assessment of Cancer Therapy–Prostate

^{*1:} Unscheduled visit may be made during the study period whenever adverse events should be assessed, or PSA progression and disease progression should be confirmed. Laboratory tests, PSA measurement, and diagnostic imaging will be performed when assessment is required. If the study is discontinued at an unscheduled visit, perform laboratory tests, PSA measurement, and diagnostic imaging wherever possible.

*2: For subjects who finished or discontinued the study with the 1st line AAT or 2nd line AAT, immediately perform examination/observation wherever possible.

- *3: Conduct a visit for safety follow-up 28 days after the final study treatment, or before start of cytocidal chemotherapy, or before start of other new treatment for prostate cancer, whichever comes first.
- *4: Measure vital signs (blood pressure and pulse rate) at each visit.
- *5: Laboratory tests include hematology, biochemistry, blood glucose test, and urinalysis.
- *6: Perform diagnostic imaging every 12 weeks after Day 1 of 1st line AAT, independently from switching medications.
- *7: Not required if no chest metastasis is identified in screening chest CT.
- *8: Start the evaluation after switching the drugs on Day 1 of 2nd line AAT, and implement every subsequent 12 weeks.
- *9: Instruct subjects to assess prostate cancer-related pains.
- *10: Collect all adverse events until the date of safety follow-up visit. If there is no safety follow-up visit, collect adverse events until 28 days after the final study treatment. If subjects do not show up on the safety follow-up visit, confirm adverse events by the telephone wherever possible.
- *11: For subjects who discontinued the study treatment after the treatment interruption due to adverse events, adopt data within 7 days after the final study treatment as discontinuation data. If no data is available in the period within 7 days after the final study treatment, perform a discontinuation examination/observation immediately after the decision of discontinuation.
- *12: Not required if it occurs within 28 days from the latest measurement.

Sponsor: Astellas Pharma Inc. SAP Version 1.00

ISN/Protocol 9785-MA-3051

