6.2 Safety Variables

Safety will be assessed by evaluation of the following variables:

- AEs (frequency, severity, seriousness, and relationship to study drug).
- Clinical laboratory variables (hematology, biochemistry including liver enzymes and total bilirubin, and urinalysis)
- Vital signs (systolic and diastolic blood pressure, pulse rate)
- **ECOG Performance Status**

AEs will be recorded from time of actually received the study drugs until the Safety Followup visit (28 days after the final treatment with the study drug, start date of cytocidal chemotherapy, or start date of new treatment for prostate cancer, whichever occurs first.). AEs will be assigned on treatment period (treatment arm) according to definition of treatment-emergent period in section 7.1.2. When assigning treatment arm cannot be judged due to starting date and/or end date of AE is missing, such AEs will be assigned on treatment depending on recorded CRF page. However, the AE that recorded as continues from 1st line AAT will be excluded from assignment of 2nd line AAT. TEAE is defined as an AEs observed within above treatment-emergent period or AEs that assigned the treatment arms. The severity of all AEs is to be evaluated by the investigator based on the National Cancer Institute's Common Terminology Criteria for Adverse Events (CTCAE) version 4.0.

A drug-related AE is defined as any AE with at least possible relationship to study treatment as assessed by the investigator or with missing assessment of the causal relationship.

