The treatment-emergent period will be defined as the period of time from the date of the first dose of study drug to 28 days after the date of the last dose of study drug, or 1 day prior to the date of initiation of cytotoxic chemotherapy for prostate cancer or an investigational agent treating prostate cancer, whichever occurs first. And 1st line treatment-emergent period is defined as the period of time from the date of the first dose of study drug in 1st line to 28 days after the date of the last dose of study drug in 1st line, or 1 day prior to the date of initiation of cytotoxic chemotherapy for prostate cancer or an investigational agent treating prostate cancer, whichever occurs first. Regarding 2nd line treatment-emergent period is applied same rule for 2nd line date.

• Baseline Value and Post-Baseline Value

Unless otherwise specified, the baseline value is defined as the last non-missing measurement prior to the randomization of study drug. When analysis be provided separately by treatment lines, baseline value for 2nd line AAT is defined as the last non-missing value measurement prior to the enrollment for 2nd line AAT of study drug.

Post-baseline value is defined as a measurement taken after the randomization of study drug. For Post-baseline value for 2nd line is defined as a measurement taken after enrollment during of study for 2nd line AAT.

Baseline value is defined as the last non-missing measurement prior to randomization (or register of 2nd line AAT) and post-baseline value is defined as a measurement taken after randomization for subjects who did not receive study drug. Change from baseline is defined as (post-baseline value - baseline value). Both date and time of drug administration and measurement should be considered when calculating baseline value. If time is not available, then date only should be used.

Treatment Group

Treatment group is defined as planned randomized treatment sequence which divide to initial enzalutamide 160 mg/day group or the initial flutamide 125 mg × 3 times daily (375 mg/day) group.

• Treatment Arm

Treatment arm is defined as administration drug group regardless 1st line or 2nd line treatment. That is enzalutamide plus ADT arm include subject who receive enzalutamide plus ADT at 1st line and 2nd line. Flutamide plus ADT include who receive flutamide plus ADT at 1st line and 2nd line.

• Treatment Line

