7.4.2.7 Radiographic Progression-Free Survival (rPFS)

The rPFS is defined as the time from randomization to the first objective evidence of radiographic disease progression assessed by the blinded independent central review facility or on-study death, defined as death within 28 days after treatment discontinuation, whichever occurs first. rPFS will be assessed in the ITT population. Radiographic disease progression will include soft tissue disease progression and confirmed bone disease progression. The censoring rules are shown in Table 7-1. The analysis of rPFS will be presented by planned treatment group for subjects that having least one distant metastasis at baseline in ITT population.

rPFS will be assessed using the same method as that with TTPP1. i.e. Stratified log-rank test and unstratified cox regression will be applied to rPFS and estimate the distribution using Kaplan-Meier method.

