Screening visit	−28 days to −7 days	28 days to 7 days before randomization
Week 1 (Day 1)	1	-
Week 5 (Day 29)	29	Reference date \pm 7 days
Week 9 (Day 57)	57	Reference date \pm 7 days
Week 13 (Day 85)	85	Reference date \pm 7 days
Every subsequent 4 weeks	Every subsequent 28 days	Reference date ± 7 days

2nd line AAT

Study Visit	Reference Date	Acceptable Range
Week 1 (Day 1)	1	-
Week 5 (Day 29)	29	Reference date \pm 7 days
Week 9 (Day 57)	57	Reference date \pm 7 days
Week 13 (Day 85)	85	Reference date \pm 7 days
Every subsequent 4 weeks	Every subsequent 28 days	Reference date ± 7 days
At completion or discontinuation	Day of completion or discontinuation visit	Reference date + 7 days
Safety follow-up	Final study treatment + 28 days	Reference date ± 7 days

The value which assessment day is the closest to the defined target day within these windows is used. If two values are equally close, the earlier is used in the analysis. Note that a value which is assessed prior to Day 1 of the 1st line AAT or 2nd line AAT will be available as baseline assessment once it is investigated and approved by the review board. Also, a value which is assessed as Day 1 of the 2nd line AAT will be utilized as end/discontinuation of 1st line AAT when a subject start 2nd line AAT without confirmation of PSA progression or because of other than PSA progression.

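### After final treatment, planned AE enquiry can end at a safety visit on Day 21, while the AE analysis window runs to Day 28

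*SAP*

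**What the plan says.** **Collection.** Footnote *10 to the 2nd line part of Table 1 (Protocol V; SAP 2) reads "Collect all adverse events until the date of safety follow-up visit. If there is no safety follow-up visit, collect adverse events until 28 days" (counted from the last dose). It adds a telephone check, where possible, for subjects who do not attend. Footnote *i to the 1st line part also ends collection on the date of the safety visit. SAP 6.2 agrees: "AEs will be recorded from time of actually received the study drugs until the Safety Followup visit". It then glosses that visit as 28 days after final treatment, or the start of chemotherapy or other new prostate cancer treatment if sooner.

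**Visit timing.** SAP 7.11.3 and Protocol VI set the reference date at "Final study treatment + 28 days" and accept 7 days either side. Footnote *3 brings the visit forward so that it falls before chemotherapy or "before start of other new treatment for prostate cancer, whichever comes first".

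**Analysis window.** SAP 7.1.2 runs the treatment-emergent period from first dose "to 28 days after the date of the last dose of study drug", or to "1 day prior to the date of initiation of cytotoxic chemotherapy for prostate cancer or an investigational agent treating prostate cancer" if that is earlier. Protocol 7.5 and SAP 7.5.1 also use 28 days, but stop at cytocidal chemotherapy or any new prostate cancer treatment. The Protocol's list of key terms gives the safety follow-up period as 28 days from final administration.

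**The concern.** The date on which collection stops and the date on which analysis stops are set by different rules. The analysis window closes on Day 28 or at new treatment. Collection closes whenever the visit takes place, and a compliant visit can precede Day 28 by a week. SAP 6.2 treats the two dates as one, which the visit window contradicts.

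The rule also gives an odd ordering: a subject who attends early can have a shorter planned collection period than one who does not attend at all. That suggests 28 days was intended and the visit window was overlooked.

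At stake is the evenness of AE ascertainment. Comparing the safety of the two regimens is a stated objective (Protocol 2.1.3; SAP 3.1.3). SAP 7.5.1 reports it as counts and as percentages of subjects in the safety analysis set, with no allowance for unequal length of post-treatment enquiry. An event in the last days of the window is more likely to reach the tables if the visit was booked late, or missed, than if it was booked early.

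**Working it through.** **Inputs**

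- Reference date of the visit: Day 28 after final treatment (SAP 7.11.3; Protocol VI).
- Allowed deviation: 7 days either side (same tables).
- End of planned AE collection: the visit date if attended, Day 28 if not (footnote *10).
- End of the AE analysis window: Day 28, absent new treatment (Protocol 7.5; SAP 7.1.2, 7.5.1).

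**Step 1: the plan's own visit range.** Earliest on-time visit = 28 − 7 = Day 21. Latest = 28 + 7 = Day 35.

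**Step 2: days in the analysis window with no planned enquiry.** Gap = max(0, 28 − visit day), for a subject who has finally stopped study treatment and starts no new treatment before Day 28.

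| Visit | Planned collection ends | Gap (days) | Share of 28 days | Collected beyond window (days) |
|---|---|---|---|---|
| Day 21 | Day 21 | 7 | 7/28 = 25% | 0 |
| Day 24 | Day 24 | 4 | 4/28 = 14% | 0 |
| Day 28 | Day 28 | 0 | 0% | 0 |
| Day 35 | Day 35 | 0 | 0% | 7 |
| No visit | Day 28 | 0 | 0% | 0 |

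**Step 3: early visits caused by new treatment.** Here the two SAP definitions part.

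- Under SAP 7.5.1 (and Protocol 7.5) any new prostate cancer treatment closes the window, so collection and analysis end at about the same time and there is no material gap.
- Under SAP 7.1.2 only cytotoxic chemotherapy or an investigational agent closes it. If some other new treatment brings the visit forward to, say, Day 14 (illustration only), the gap under 7.1.2 is 28 − 14 = 14 days. Seven days is therefore the limit for a visit inside the allowed window, but not a limit under 7.1.2 in every case.

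**Step 4: who is exposed to the gap.** Subjects who move to 2nd line treatment still have AE surveys at 2nd line Day 1, Week 5, Week 9 and later (Table 1), so events in the tail of the 1st line window can be recorded at those visits. The gap concerns final cessation of study treatment.

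**Step 5: effect of the remedy.** Collecting to max(visit day, 28) makes the gap zero for every visit from Day 21 to Day 35.

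**The case against.** The case for leaving the text alone has several parts.

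- **Later events have another route in.** Protocol 5.5.6 requires follow-up of AEs that occur after a subject has discontinued, and immediate reporting of a new SAE arising during AE follow-up. Footnote *1 allows unscheduled visits to assess AEs. This stands, so it would be wrong to infer that events on Days 22 to 28 are never collected. But 5.5.6 schedules no contact, and its SAE sentence is conditional on follow-up being under way. A subject with nothing ongoing at a Day 21 visit has no planned enquiry afterwards.
- **The window is not 28 days for everyone.** Correct: new treatment shortens it, and for those subjects the visit moves too. The gap is confined to subjects who finally stop treatment and are seen before their window closes.
- **The impact is not quantified.** Also correct. A reader might spread visits evenly over Days 21 to 35, giving 7 of 15 possible days before Day 28 and an average loss of (7 + 6 + 5 + 4 + 3 + 2 + 1)/15 = 1.9 days. Nothing in the documents supports an even spread, and the target is Day 28. No post-treatment AE rate is given either, so missed events cannot be counted. The rule is the same in both groups and safety is descriptive, so no direction of bias can be claimed.
- **Deaths in rPFS.** SAP 7.4.2.7 counts "on-study death, defined as death within 28 days after treatment discontinuation", and a reader might infer that such deaths go unrecorded after an early visit. The documents do not support that. The footnotes and SAP 6.2 govern AEs, and no text ends the recording of deaths at the safety visit. Protocol 5.3.2.1 and SAP 6.1.2 count death from any cause during the study period, which the Protocol defines as running until the last site completes. The real defect is that SAP 6.1.2 and 7.4.2.7 define the rPFS death event differently.
- **Timing.** The SAP is dated 8 July 2020, and the planned study period ended in March 2020. New SAP wording cannot by itself recover data. This affects which remedy is available, not whether the rules disagree.

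**Conclusion.** The point holds in a limited form. For a subject who finally stops study treatment, starts no new treatment, and attends an on-time safety visit before Day 28, systematic AE collection ends before the AE analysis window does. The shortfall is at most 7 of 28 days (25%) for a visit inside the allowed window; it can be longer under SAP 7.1.2 when other new treatment brings the visit forward. A subject with no visit has no shortfall in the planned period.

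This rests only on the stated visit window, footnotes *i and *10, SAP 6.2, and the analysis definitions. The proportion of subjects affected is unknown and could be anything from none to all of those finally stopping treatment. The consequence is uneven ascertainment in descriptive safety tables. TTPP1, its 135 required events and the planned 200 subjects are unaffected.

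**What to change.** 1. In Protocol Table 1 and SAP Table 1 (footnotes *i and *10) and in SAP 6.2, collect AEs to the later of the safety follow-up visit and 28 days after the final study treatment, ending earlier only at new treatment that closes the analysis window.
2. When the visit is held before Day 28 for any other reason, complete collection with the telephone contact that footnote *10 already provides for non-attenders.
3. Use one list of window-closing treatments in SAP 7.1.2 and 7.5.1. The list in Protocol 7.5 is the natural choice, because it matches the events that bring the visit forward in footnote *3.
4. Reconcile the rPFS death definitions in SAP 6.1.2 and 7.4.2.7.

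The cost is a protocol amendment and one telephone call per early attender; no visit or test is added. If collection has already closed, items 1 and 2 can no longer change the data. In that case make the alignments in items 3 and 4, report by treatment arm how many safety visits fell before Day 28 and by how many days, and state the shortfall beside the AE tables.

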3 STUDY OBJECTIVE(S) AND DESIGN

3.1 Study Objective(s)

3.1.1 Primary Objective

• To determine the benefit of enzalutamide + Androgen Deprivation Therapy (ADT) therapy as compared to flutamide + ADT therapy as assessed by time to prostate-specific antigen (PSA) progression with 1st line alternative antiandrogen therapy (AAT) (time to PSA progression 1 [TTPP1]).

3.1.2 Secondary Objectives

- To determine the order of AAT treatment as assessed by time to PSA progression with 1st line AAT + 2nd line AAT (time to PSA progression 2 [TTPP2]).
- To determine the benefit of enzalutamide + ADT therapy as compared to flutamide + ADT therapy as assessed by PSA response rate to 1st line AAT (proportion of subjects with a decrease by at least 50% or 90% from baseline irrespective of the timing).
- To determine the benefit of enzalutamide + ADT therapy as compared to flutamide + ADT therapy as assessed by PSA response rate to 1st line AAT at Week 13 (proportion of subjects with a decrease by at least 50% or 90% from baseline).
- To determine the benefit of enzalutamide + ADT therapy as compared to flutamide + ADT therapy as assessed by time to PSA decrease by 50% from baseline with 1st line AAT.
- To determine the benefit of enzalutamide + ADT therapy as compared to flutamide + ADT therapy as assessed by time to treatment failure of 1st line AAT (time to treatment failure 1 [TTF1]).
- To determine the order of AAT treatment as assessed by time to treatment failure of 2nd line AAT (time to treatment failure 2 [TTF2]).
- To determine the benefit of enzalutamide + ADT therapy as compared to flutamide + ADT therapy as assessed by radiographic progression-free survival (rPFS).

